### 3. PLANNED ANALYSES

#### 3.1. Interim Analyses

A summary of integrated safety data from MEA116841 and 201607 (compassionate use programme) was conducted to support mepolizumab EGPA submissions in the US and Japan, using a cut-off date of 05-SEP-2016 (GlaxoSmithKline Document Number: [2017N320079\\_00](#)).

Further interim analyses may be conducted, as required.

This RAP contains details of analyses proposed for future interim analyses as well as the final study report. Access to the results from such interim analyses will not be confidential. Specifically the results will be provided to the study team and GSK governance boards, and may be provided to external investigators and to regulatory authorities.

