### 4. ANALYSIS POPULATIONS

Population	Definition / Criteria	Analyses Evaluated
All Subjects Enrolled	Comprises all subjects enrolled and for whom a record exists on the study database. This population will be used for summarising reasons for screen and run-in failures.	Study Population
Safety	Comprise of all subjects who receive at least one dose of mepolizumab	
 
• Study Population
 
• Safety
 

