## 7. SAFETY ANALYSES

The safety analyses will be based on the Safety population, unless otherwise specified.

The LAP comprises a clinical trial (MEA116841) and compassionate use programme (201607) restricted to subjects who participated in MEA115921. The compassionate use programme (CUP) was conducted under a guidance document which mirrored the objectives of MEA116841. Since 201607 was run as a CUP, the treating physician was the responsible party. Per local legal requirements, serious adverse event reporting was required at a minimum. Furthermore, GSK did not monitor CUP 201607, and therefore verification that all non-serious adverse events (AEs) were reported is not possible.

For this reason, summaries of adverse events are reported separately for MEA116841 and 201607, with the exception of serious adverse events, which are additionally reported using combined MEA116841 and 201607 data.

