## 9.2. Appendix 2: Study Phases and Treatment Emergent Adverse Events

### 9.2.1. Study Phases

Treatment State	Definition
Pre-Treatment	AE Start Date/Time < Study Treatment Start Date/Time
On-Treatment	Study Treatment Start Date/Time $\leq$ AE Start Date/Time $\leq$ Study Treatment Stop Date + 28 days
Post-Treatment	AE Start Date > Study Treatment Stop Date + 28 days

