**NOTES:**

- If the study treatment stop date is missing then the AE will be considered to be On-Treatment.

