### 9.7.5. Safety Tables

Safety: Tables					
No.	Population	IDSL / Example Shell	Title	Programming Notes	Deliverable [Priority]
Exposure					
3.1.	Safety	mid_mepo_egpa_lap /interim1 Table 3.1	Summary of Exposure to Study Treatment	
 
MEA116841
 
201607
 
MEA116841 + 201607
 
	IA , SAC
3.2.	Safety	mid_mepo_egpa_lap /interim1 Table 3.2	Summary of Number of Treatment Administered	
 
MEA116841
 
201607
 
MEA116841 + 201607
 
	IA , SAC
Adverse Events (AEs)					
3.3.	Safety	AE1	Summary of On-Treatment Adverse Events by System Organ Class and Preferred Term	
 
MEA116841
 
201607
 
	IA , SAC
3.4.	Safety	AE1	Summary of Post-Treatment Adverse Events by System Organ Class and Preferred Term	
 
MEA116841
 
201607
 
	IA , SAC
3.5.	Safety	AE3	Summary of Common (>=3%) Adverse Events by Preferred Term	
 
MEA116841
 
201607
 
	IA , SAC
3.6.	Safety	AE1	Summary All Drug-Related Adverse Events by System Organ Class and Preferred Term	
 
MEA116841
 
201607As 3.1 notes
 
	IA , SAC
3.7.	Safety	AE3	Summary of Adverse Events Leading to Permanent Discontinuation of Study Treatment or Withdrawal from Study by Preferred Term	
 
MEA116841
 
201607For studies with few events/participants, listing is sufficient.
 
	IA , SAC

Safety: Tables					
No.	Population	IDSL / Example Shell	Title	Programming Notes	Deliverable [Priority]
3.8.	Safety	AE15	Summary of Common (>=3%) Non-serious Adverse Events by System Organ Class and Preferred Term (Number of Participant and Occurrences)	
 
MEA116841
 
201607Common' to be defined by study/project team. For studies with very few events/participants, listing is sufficient: discuss this option with your disclosure representative.
 
	IA , SAC
3.9.	Safety	AE5A	Summary of On-Treatment Adverse Events by System Organ Class and Preferred Term and Maximum Intensity	
 
MEA116841
 
201607Common' to be defined by study/project team. For studies with very few events/participants, listing is sufficient: discuss this option with your disclosure representative.
 
	IA , SAC

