Serious and Other Significant Adverse Events					
3.10.	Safety	AE1	Summary of Pre-Treatment Serious Adverse Events by System Organ Class and Preferred Term	
 
MEA116841
 
201607For studies with few events/participants listing is sufficient: discuss this option with your disclosure representative.
 
MEA116841 + 201607
 
	IA , SAC

Safety: Tables					
No.	Population	IDSL / Example Shell	Title	Programming Notes	Deliverable [Priority]
3.11.	Safety	AE1	Summary of On-Treatment Serious Adverse Events by System Organ Class and Preferred Term	
 
MEA116841
 
201607For studies with few events/participants listing is sufficient: discuss this option with your disclosure representative.
 
MEA116841 + 201607
 
	IA , SAC
3.12.	Safety	AE1	Summary of Post-Treatment Serious Adverse Events by System Organ Class and Preferred Term	
 
MEA116841
 
201607For studies with few events/participants listing is sufficient: discuss this option with your disclosure representative.
 
MEA116841 + 201607
 
	IA , SAC
3.13.	Safety	AE16	Summary of Serious Adverse Events by System Organ Class and Preferred Term (Number of Participants and Occurrences)	Required for data disclosure 
 
MEA116841
 
201607For studies with few events/participants listing is sufficient: discuss this option with your disclosure representative.
 
MEA116841 + 201607
 
	IA , SAC

Safety: Tables					
No.	Population	IDSL / Example Shell	Title	Programming Notes	Deliverable [Priority]
3.14.	Safety	AE1	Summary of On-Treatment Non-Fatal Serious Adverse Events by System Organ Class and Preferred Term	
 
MEA116841
 
201607For studies with few events/participants listing is sufficient: discuss this option with your disclosure representative.
 
MEA116841 + 201607
 
	IA , SAC
3.15.	Safety	AE1	Summary of Fatal Serious Adverse Events by System Organ Class and Preferred Term	
 
MEA116841
 
201607For studies with few events/participants listing is sufficient: discuss this option with your disclosure representative.
 
MEA116841 + 201607
 
	IA , SAC

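### On the natural reading of the SAP, Tables 3.4 and 3.12 dilute post-treatment AE and SAE percentages at any interim held while some subjects are still being dosed

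*SAP*

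**What the plan says.** SAP Section 9.7.5 lists Table 3.4, "Summary of Post-Treatment Adverse Events by System Organ Class and Preferred Term", and Table 3.12, "Summary of Post-Treatment Serious Adverse Events by System Organ Class and Preferred Term". Both have Safety in the population column, use shell AE1 and are deliverables at interim and at the end. Table 3.4 is produced for MEA116841 and 201607 separately; Table 3.12 adds a combined version.

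Section 4 defines the Safety population: "Comprise of all subjects who receive at least one dose of mepolizumab". Section 7 makes it the default: "The safety analyses will be based on the Safety population, unless otherwise specified". Nothing else is specified for these two tables.

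Section 9.2.1 defines a post-treatment event by "AE Start Date > Study Treatment Stop Date + 28 days", and the note beneath it adds: "If the study treatment stop date is missing then the AE will be considered to be On-Treatment".

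On timing, Section 3.1 says "Further interim analyses may be conducted, as required", and that "This RAP contains details of analyses proposed for future interim analyses as well as the final study report". Section 3.2 places the final analysis after every participant has completed.

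**The concern.** Under Protocol Sections 4.1 and 5.3, treatment is open-ended: it runs until local licensing, the end of development in EGPA or an individual stopping criterion, with a fixed end date for the UK. An interim may therefore fall while some subjects are still being dosed. Those subjects have no post-treatment time, so they can add nothing to the numerator of Tables 3.4 and 3.12, yet they remain in N.

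The resulting percentage mixes two things: how often events follow stopping, and how many subjects have stopped. It can rise from one interim to the next, or differ between MEA116841 and 201607 or between the prior-placebo and prior-mepolizumab columns (SAP Section 5.1), with no difference in risk. Protocol Section 9.1 gives the interims the purpose of informing the risk-benefit assessment, and SAP Section 3.1 allows results to go to regulators and outside investigators. A reader who sees a low post-treatment percentage could take the off-drug period to be quieter than it was.

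**Working it through.** The plan states no post-treatment percentage, no count of subjects stopped and no sample size for an interim, so there is no figure to reproduce. The check is whether the SAP's own rules produce the dilution, and how large it could be.

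**Step 1: who can be in the numerator.** By Section 9.2.1, only a subject with a treatment stop date and an event starting after that date plus 28 days. A subject with no stop date has all events from first dose onward classed as on-treatment, so none can be post-treatment.

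**Step 2: who is in the denominator.** The population column gives Safety, meaning everyone dosed. Section 9.3.2 says categorical data are shown with N, n, frequency and percentage. Shell AE1 is not reproduced, so a percentage over the Safety N is an inference, though the natural one.

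**Step 3: the relation.** Let f = (Safety subjects followed beyond last dose + 28 days) / (all Safety subjects) at the cut-off. Then:

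- displayed % = f × (% among subjects at risk)
- understatement factor = 1/f

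**Step 4: the range.** f is not in the documents. The last column assumes, for illustration only, that 30% of those at risk have an event.

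| f | 1/f | Shown when 30% of those at risk have an event |
|---|---|---|
| 0.10 | 10 | 3.0% |
| 0.25 | 4 | 7.5% |
| 0.50 | 2 | 15.0% |
| 0.75 | 1.33 | 22.5% |
| 0.90 | 1.11 | 27.0% |
| 1.00 | 1 | 30.0% |

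In counts, with an assumed 100 dosed and 3 with a post-treatment SAE, the table shows 3/100 = 3%. Among those at risk it is 3/10 = 30%, 3/25 = 12% or 3/50 = 6% when 10, 25 or 50 subjects are at risk. A factor of 3 or more needs f of one third or less.

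**Step 5: is it repaired elsewhere?** The exposure-adjusted tables (3.42 to 3.46) cover on-treatment or drug-related events; none gives a post-treatment rate or post-treatment person-time. Table 1.2 reports treatment status at the same deliveries, but not how many subjects are more than 28 days past last dose.

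**Step 6: the final analysis.** All participants have completed by then (Section 3.2), so no subject is still dosing. The design figure in SAP Section 2.3 lets safety follow-up take place before marketed product starts, as an alternative to 12 weeks after last dose. A subject whose follow-up ended by day 28 stays in N with no post-treatment window. Those followed for the full 12 weeks have 84 − 28 = 56 days.

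**The case against.** A reader might infer that the figures are diluted several-fold at every interim because most subjects will still be on drug. The documents do not support that. They do not say what share will have stopped at any cut-off. This SAP is based on the June 2019 protocol amendment, the 2016 interim supported submissions in the US and Japan, and supply ends country by country on licensing, so f could be high. It should also rise as subjects stop, which shrinks the dilution at later cut-offs. Further interims are optional, so there may be none. All of this stands, and it limits the size and reach of the point.

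It can also be said that the tables are descriptive with no hypotheses, and that events over everyone dosed is a legitimate quantity. That is true, but a reader will take a column headed post-treatment as describing the post-treatment period, and the SAP offers no other figure for it.

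The remaining objections stand in part:

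- Table 1.2 and the listings let a reader approximate the number at risk, but Table 1.2 alone does not show who has passed day 28.
- The programming notes for Table 3.12 allow a listing when events or participants are few; Table 3.4 carries no such note.
- A corrected percentage still cannot be set directly against an on-treatment one, because on-treatment time is open-ended and scheduled post-treatment time is about 56 days.
- Programme 201607 was not monitored by the sponsor (SAP Section 7), so last-contact dates there cannot be taken for granted.

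**Conclusion.** The point holds as a denominator problem of known direction and unknown size. At any interim held while subjects are still being dosed, the percentages in Tables 3.4 and 3.12 are f times those among subjects at risk, and so are too low whenever f is below 1 and any such event has occurred. Over the range shown, the understatement runs from 10-fold at f = 0.10 to 1.1-fold at f = 0.90. At the final analysis it remains only for subjects whose follow-up ended by day 28 after last dose, such as some who move to marketed product.

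This rests on two assumptions: that shell AE1 divides by the N of the stated population, and that at least one interim is held while dosing continues. No hypothesis test is affected. It is an inexpensive improvement to how off-drug safety is reported.

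**What to change.** For Tables 3.4 and 3.12, in every column and at interim and final, use as denominator the Safety subjects with a recorded treatment stop and follow-up beyond last dose plus 28 days at the cut-off. The recorded stop matters because, with visit windows of 7 days either way, a subject still on the 4-weekly schedule can be more than 28 days past the latest dose. Print this N beside the Safety N in each column, and give these subjects' total post-treatment days, counted from day 29 after last dose to last contact or cut-off, whichever comes first.

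Where last-contact dates are not available, possibly in 201607, define the flag from the last dose date and the cut-off date and footnote this. That N is then an upper limit, because it includes subjects whose follow-up ended early, and days counted to the cut-off are likewise a maximum. A further footnote should say that these percentages are not comparable with the on-treatment ones, because observation time differs.

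The change needs one date-derived flag and a sentence each in SAP Sections 4 and 9.7.5. The downside is small denominators at early interims: with 10 subjects at risk, one event shows as 10%. Keeping the Safety N alongside lets a reader see why.

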### 1.1. RAP Amendments

All revisions since the previous approved RAP (dated 26-Sep-2016) are listed below:

RAP Section	Amendment Details
All	Formatting changes to fit RAP_Template_Master_v2 (8-Aug-2017)
3.1 Interim Analyses	Details of previous interim analysis (5-Sep-2016 cut-off date) were added
4.1 Protocol Deviations	Reference added to updated PDMP
7.1 Safety Analyses	Added text providing additional information regarding adverse event reporting for MEA116841 and 201607
9.7.4 Study Population Tables	
 
• Removed “Summary of Reasons for Screen and Run-In Failure” (Rationale: there was only one occurrence and these data are included in the listings)
 
• Removed “Summary of Inclusion/Exclusion Criteria” (Rationale: there was only one occurrence and these data are included in the listings)
 
• Added “Summary of Age Ranges” (Required as per revised RAP template)
 
• Added “Summary of Serious Adverse Events by System Organ Class and Preferred Term (Number of Participants and Occurrences)” (Required for disclosure purposes).
 

RAP Section	Amendment Details
	

• Added “Summary of Non-Serious Drug-Related Adverse Events by Overall Frequency” (Required for Plain language Summaries)

• Added “Summary of Non-Serious Drug-Related Adverse Events by Overall Frequency” (Required for Plain language Summaries)

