3.16.	Safety	AE1	Summary of Drug-Related Non-Fatal Serious Adverse Events by System Organ Class and Preferred Term	
 
MEA116841
 
201607For studies with few events/participants listing is sufficient: discuss this option with your disclosure representative.
 
MEA116841 + 201607
 
	IA , SAC

Safety: Tables					
No.	Population	IDSL / Example Shell	Title	Programming Notes	Deliverable [Priority]
3.17.	Safety	AE1	Summary of Drug-Related Fatal Adverse Events by System Organ Class and Preferred Term	
 
MEA116841
 
201607For studies with few events/participants listing is sufficient: discuss this option with your disclosure representative.
 
MEA116841 + 201607
 
	IA , SAC
3.18.	Safety	AE3	Summary of Non-Serious Drug-Related Adverse Events by Overall Frequency	
Required for Plain Language Summary
 
 
MEA116841
 
201607For studies with few events/participants listing is sufficient: discuss this option with your disclosure representative.
 
MEA116841 + 201607
 
	IA , SAC
3.19.	Safety	AE3	Summary of Serious Drug-Related Adverse Events by Overall Frequency	
Required for Plain Language Summary
 
 
MEA116841
 
201607For studies with few events/participants listing is sufficient: discuss this option with your disclosure representative.
 
MEA116841 + 201607
 
	IA , SAC

Safety: Tables					
No.	Population	IDSL / Example Shell	Title	Programming Notes	Deliverable [Priority]
3.20.	Safety	mid_mepo_egpa_lap /interim1 Table 3.16	Summary of All Cardiovascular Events Reported by the Investigator	
 
MEA116841
 
201607 For studies with few events/participants listing is sufficient: discuss this option with your disclosure representative.
 
MEA116841 + 201607
 
	IA , SAC
Adverse Events of Special Interest					
3.21.	Safety	mid_mepo_egpa_lap /interim1 Table 3.17	Summary of On-Treatment Adverse Events of Special Interest: Systemic Reactions	
 
MEA116841
 
201607
 
	IA , SAC

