3.40.	Safety	mid_mepo_egpa_lap /interim1 Table 3.36	Summary Profile of On-Treatment Adverse Events of Special Interest: Serious Cardiac, Vascular and Thromboembolic	
 
• MEA116841
 
• 201607
 
	IA , SAC
3.41.	Safety	mid_mepo_egpa_lap /interim1 Table 3.37	Summary Profile of On-Treatment Adverse Events of Special Interest: Serious Ischemic Events	
 
• MEA116841
 
• 201607
 
	IA , SAC

Safety: Tables					
No.	Population	IDSL / Example Shell	Title	Programming Notes	Deliverable [Priority]
Exposure-Adjusted Adverse Events					
3.42.	Safety	mid_mepo_egpa_lap /interim1 Table 3.38	Summary of Exposure Adjusted On-Treatment Adverse Events	
 
• MEA116841
 
• 201607
 
	IA , SAC
3.43.	Safety	mid_mepo_egpa_lap /interim1 Table 3.39	Summary of Exposure Adjusted Most Frequent On-Treatment Adverse Events Reported by 3% or More Subjects In Any Treatment Group	
 
• MEA116841
 
• 201607
 
	IA , SAC
3.44.	Safety	mid_mepo_egpa_lap /interim1 Table 3.40	Summary of Exposure Adjusted Drug Related Adverse Events	
 
• MEA116841
 
• 201607
 
	IA , SAC
3.45.	Safety	mid_mepo_egpa_lap /interim1 Table 3.41	Summary of Exposure Adjusted On-Treatment Adverse Events Leading To Permanent Discontinuation of Study Drug or Withdrawal From Study	
 
• MEA116841
 
• 201607
 
	IA , SAC
3.46.	Safety	mid_mepo_egpa_lap /interim1 Table 3.42	Summary of Exposure Adjusted On-Treatment Serious Adverse Events	
 
• MEA116841
 
• 201607
 
	IA , SAC
3.47.	Safety	mid_mepo_egpa_lap /interim1 Table 3.43	Summary of On-Treatment Adverse Events by Age Category	
 
• MEA116841
 
• 201607
 
	IA , SAC
3.48.	Safety	mid_mepo_egpa_lap /interim1 Table 3.44	Summary of On-Treatment Adverse Events by Sex	
 
• MEA116841
 
• 201607
 
	IA , SAC
3.49.	Safety	mid_mepo_egpa_lap /interim1 Table 3.45	Summary of On-Treatment Adverse Events by Race	
 
• MEA116841
 
• 201607201607
 
	IA , SAC

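### Table 3.18 pools non-serious drug-related adverse events from MEA116841 and 201607, although SAP Section 7 allows pooling only for serious adverse events

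*SAP*

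**What the plan says.** SAP Section 7 (Safety Analyses) sets the rule. Adverse event summaries are presented separately for MEA116841 and 201607, "with the exception of serious adverse events, which are additionally reported using combined MEA116841 and 201607 data". The section also gives the reason. In 201607 the treating physician was the responsible party, reporting of serious events was the minimum requirement, and the sponsor did not monitor the programme, so "verification that all non-serious adverse events (AEs) were reported is not possible".

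SAP 9.7.5 then lists the tables. Table 3.18 is "Summary of Non-Serious Drug-Related Adverse Events by Overall Frequency", marked "Required for Plain Language Summary". Its programming notes list three displays: MEA116841, 201607, and MEA116841 + 201607. It is due at both interim and final reporting.

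Two related tables list the two separate displays only:
- Table 3.8, the other non-serious table: "Summary of Common (>=3%) Non-serious Adverse Events by System Organ Class and Preferred Term (Number of Participant and Occurrences".
- Table 3.44: "Summary of Exposure Adjusted Drug Related Adverse Events".

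**The concern.** The rule in Section 7 exists to keep non-serious events from the two sources apart, and Table 3.18 consists entirely of such events. Following the display list produces a pooled percentage that Section 7 excludes. Following Section 7 means ignoring a line in the list.

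The pooled column would count every 201607 subject in its denominator, while its numerator would hold only those non-serious events that physicians chose to report. Any shortfall lowers the percentage. The table is intended for a plain language summary, whose readers are unlikely to see the caveat in Section 7, and the SAP does not say which of the three displays supplies that figure. SAP 3.1 adds that interim results may go to external investigators and regulatory authorities.

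**Working it through.** The plan gives no figure to reproduce. The check compares Section 7 with the programming notes of every adverse event table in SAP 9.7.5, then works out the direction of any error.

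**Count of tables**
- Adverse event tables: 3.3 to 3.49, so 49 − 3 + 1 = 47.
- Separate displays only in the bullets: 3.3 to 3.9 (7) and 3.21 to 3.49 (29), so 7 + 29 = 36. Table 3.6 is placed here on its bullets alone (see the last paragraph).
- Pooled display also listed: 3.10 to 3.20, which is 11. Check: 36 + 11 = 47.

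**Content of the 11 pooled tables**
- Serious or fatal events only: 3.10 to 3.17 (8) and 3.19 (1), so 9. These fit the Section 7 exception.
- Wholly non-serious: 3.18, so 1. This conflicts with the rule.
- Not limited to serious events by its title: 3.20, so 1. Check: 9 + 1 + 1 = 11.

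**Direction of any error**

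Let f be the share of subjects in 201607 and c the proportion of 201607 subjects with such an event for whom it was recorded (0 ≤ c ≤ 1). Assume complete capture in MEA116841. With the same true percentage p in both sources:

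observed pooled = (1 − f)p + f·c·p = p[1 − f(1 − c)]

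observed ÷ true = 1 − f(1 − c)

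The ratio runs from 1 − f (nothing captured, c = 0) to 1 (complete capture, c = 1). If the true percentages differ, say p₁ in MEA116841 and p₂ in 201607, the ratio is [(1 − f)p₁ + f·c·p₂] ÷ [(1 − f)p₁ + f·p₂]. This also cannot exceed 1, so the direction does not depend on equal rates. The documents give neither f nor c, so no value is put in.

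For the 201607 display alone the ratio is c. Since 1 − f(1 − c) − c = (1 − f)(1 − c) ≥ 0, that display is at least as exposed as the pooled one. It therefore needs a footnote if it is kept.

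**Two tables that the text leaves open**

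Table 3.20 covers all cardiovascular events reported by the investigator. Protocol 12.4.3 requires the cardiovascular CRF page for both non-serious and serious events, so for MEA116841 non-serious events may well be included. What 201607 contributes is not stated. Table 3.6, "Summary All Drug-Related Adverse Events by System Organ Class and Preferred Term", has bullets for the two separate displays, but a note run on to the second bullet refers to the notes for Table 3.1, and those include a pooled display.

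**The case against.** The best defence of the pooled line is SAP Section 1, which says combined summaries will be produced from the two sources. That statement is general, and the combined disposition, demography, exposure and serious event tables satisfy it. Section 7 is the specific rule for adverse events and gives its reason. The plain language marking on Table 3.18 states a purpose and does not grant an exemption.

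It can also be said that the consequence is small. SAP 2.4 defines no hypotheses, both separate displays are planned anyway, Section 7 discloses the limitation, and the note to Table 3.18 lets a listing replace the table if events are few. All of this stands and limits the weight of the point. It does not remove the contradiction.

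Three stronger readings are tempting, and the documents do not support them:
- A reader might infer that everything else in the list tracks Section 7, so that 3.18 is a lone slip. Six serious-only tables (3.31, 3.32, 3.33, 3.40, 3.41 and 3.46) have no pooled display, and 3.20 and 3.6 are unsettled. Section 7 need not require pooling in every serious event table, but the match is not clean.
- A reader might infer from SAP 1.1 that the rule and the table were both new in this revision. The log says only "Added text providing additional information regarding adverse event reporting for MEA116841 and 201607". It does not say that the rule on separate and combined reporting was new. It also lists the non-serious plain language title twice and omits its serious counterpart, so little can rest on it.
- A reader might infer that the plain language figure must come from MEA116841 alone. The SAP defines the programme as both sources and does not settle which display feeds that summary.

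**Conclusion.** The contradiction is real: Table 3.18 lists a pooled display of wholly non-serious events, Section 7 excludes it, and no section exempts it. It is the only such table among the 11 with a pooled display, and Tables 3.8 and 3.44 show comparable content kept separate.

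The documents say that complete reporting in 201607 cannot be verified. They do not say that reporting was incomplete. The understatement is therefore a risk of unknown size, not an established bias. If it exists, incomplete capture in 201607 can only pull the pooled percentage down, assuming complete capture in MEA116841. Only descriptive reporting is affected. The point is worth fixing before the next delivery, because the correction is cheap and the table has a lay audience.

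**What to change.** For Table 3.18:
- Delete MEA116841 + 201607 from the programming notes and keep the two separate displays.
- Footnote the 201607 display to say that complete reporting of non-serious events could not be verified.
- State which display feeds the plain language summary. It should not be a pooled figure without that caveat.

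If the sponsor wants to keep the pooled display, the consistent alternative is a stated and justified exception in Section 7, with the same caveat on the pooled column.

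Queries:
- Table 3.20: confirm from its shell and the 201607 data whether the pooled display includes non-serious events. If so, limit that display to serious cardiovascular events.
- Table 3.6: confirm that only the separate displays are intended, and remove the reference to the Table 3.1 notes.

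Cost: for Table 3.18, one bullet deleted, one footnote and one sentence, with no new data. The Table 3.20 query needs a check of the shell and the data, and possibly a shell change. For Table 3.6 it is a confirmation and one deletion.
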